- Study subject will receive study drug(s) to which they are randomized. Arm A subjects will receive rVWF plus TA, while Arm B subjects will receive rVWF alone. The rVWF is given immediately before epidural or delivery, which is first. TA is given within 3 hours of delivery. If bleeding continues after 30 minutes of the first TA dose (in Arm A), a second dose of TA 1 gm IV will be given.
- Quantitative blood loss (QBL) during C-section and vaginal delivery will be calculated by the labor suite nurse and the mode of delivery will be obtained from hospital medical chart.
- Assessment for adverse events, allergic reactions, thrombosis, other bleeding
- The study subject will be given a Diary, to record lochia blood loss by pictorial blood assessment chart (PBAC), blood products, transfusion, and concomitant medications daily for up to 21 days.

Study Visit 3: Day 1 Postpartum

The visit occurs at 1 day postpartum.

- Blood draw: a 9 ml plasma sample for blood counts at UPMC University Clinical Laboratories, and VWF assays and coagulation tests by the ITxM/Vitalant Coagulation Laboratory, Pittsburgh.
- Interim medical history, new diagnoses, medications, allergies.
- Diary review: lochia blood loss by PBAC, blood products, transfusion, and concomitant medications.
- Assessment for adverse events, allergic reactions, thrombosis, other bleeding

Study Visit 4: Day 2 Postpartum

The visit occurs at 2 days postpartum.

- Blood draw: a 9 ml plasma sample for blood counts at UPMC University Clinical Laboratories, and VWF assays and coagulation tests by the ITxM/Vitalant Coagulation Laboratory, Pittsburgh.
- Interim medical history, new diagnoses, medications, allergies.
- Diary review: lochia blood loss by PBAC, blood products, transfusion, and concomitant medications.
- Assessment for adverse events, allergic reactions, thrombosis, other bleeding

Study Visit 5: Day 21, End of Study Visit

The visit occurs at 21 days postpartum, at the end of study.

- Blood draw: a 9 ml plasma sample for blood counts at UPMC University Clinical Laboratories, and VWF assays and coagulation tests by the ITxM/Vitalant Coagulation Laboratory, Pittsburgh.
- Interim medical history, new diagnoses, medications, allergies.
- Diary review: estimated lochia blood loss by PBAC, blood products, transfusion, and concomitant medications.

- Assessment for adverse events, allergic reactions, thrombosis, other bleeding.

The blood volume for all tests is 49 cc (~3 tbsp) during this 8-week trial.

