Blood Sample Storage. Blood samples will be stored indefinitely at the Hemophilia Center of Western PA under the control of [name]. Samples will be labeled with code numbers, and information linking the code numbers to the subjects' identities will be kept in a separate, locked file at the Hemophilia Center.

Adverse events. The analysis of adverse events, including allergic reaction, thrombosis, and other bleeding, will be based on the number of subjects with adverse events, and incidence rates will be calculated as the number of subjects with an event divided by the number of subjects exposed to drug. Subjects with multiple events will be counted only once in the numerator. For analysis, the highest-grade severity will be considered, and for analysis of duration, the multiple episodes will be summed. Adverse events will be summarized, and each event reported by a subject will be counted repeatedly. The corresponding incidence rates for adverse event episodes will be calculated by the number of adverse event cases over the number of doses. Adverse event incidence rates will be categorized by body system, relationship to study drug, severity of adverse event, age, sex, time of onset of adverse event, and duration of adverse event. Laboratory variables will be analyzed by descriptive statistics.

Sample Size and Power for Pilot Study

Pilot studies require a minimum of nine subjects to prevent an unnecessarily high number of subjects to receive a study drug, but a high enough number to provide insight into safety and efficacy parameters for a study drug.⁴¹ The minimum planned sample size of 20 evaluable subjects also provides adequate power to

evaluate the success and feasibility of the study.⁴¹ The study is considered successful if treatment of fewer than or equal to 6 of the 20 subjects is assessed ineffective or unsafe. The study is considered feasible if procedures, i.e. recruitment, randomization, and study drug administration can be performed successfully.

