APPENDIX

SCHEDULE OF EVENTS

Schedule of Events					
Study Week	-4	0	0	0	3
Study Visit	1	2	3	4	5
Event	32-39 Weeks'	Admission Childbirth	Day 1	Day 2	Day 21

	Gestation				
Screening, Consent	X				
Clinical Assessment					
Medical History	X		X	X	X
Vital Signs	X				
Mode of Delivery		X			
Randomization	X				
End of Study					X
Laboratory Assessment					
Blood Counts: Hemoglobin, Platelets	X	X	X	X	X
Iron Tests: Fe, TIBC, Ferritin	X				
VWF Assays: VWF:RCo, VWF:Ag, VIII:C	X	X	X	X	X
Coagulation Assays: Fibrinogen, D-dimer	X	X	X	X	X
Primary Endpoint Measure					
Quantitative Blood Loss at Delivery		X			
Secondary Endpoint Measures					
Lochial blood loss by PBAC			X	X	X
Diary: Blood products, transfusion, medications			X	X	X
Safety: Hysterectomy, thrombosis			X	X	X
Adverse Events					
Allergic reaction		X	X	X	X
Thrombosis		X	X	X	X
Bleeding (other)		X	X	X	X

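### Adverse events are to be tabulated by onset and duration, but after Day 2 the only scheduled assessment is Day 21 and the daily diary has no adverse-event item, so the tables will mix true timing with contact frequency

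*Combined protocol and SAP*

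**What the plan says.** **Planned tables.** The adverse events paragraph of Section 3.3 states: "Adverse event incidence rates will be categorized by body system, relationship to study drug, severity of adverse event, age, sex, time of onset". Duration is a further category, and a woman's repeat episodes have their durations added together. No onset windows are defined. Two denominators are given. At subject level, "incidence rates will be calculated as the number of subjects with an event divided by the number of subjects exposed to drug". At episode level, rates are "calculated by the number of adverse event cases over the number of doses". Neither uses time at risk.

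**Scheduled assessment.** Section 3.2 lists the item "Assessment for adverse events, allergic reactions, thrombosis, other bleeding" at Visits 2, 3, 4 and 5, and the Schedule of Events in the Appendix agrees. Visit 2 is admission and delivery, and Visit 3 is Day 1. For Visit 4, "The visit occurs at 2 days postpartum". For Visit 5, "The visit occurs at 21 days postpartum, at the end of study". Section 3.2 also has symptoms recorded after each infusion, which covers delivery, Day 1 and Day 2 only.

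**Diary.** At Visit 2 the woman receives a diary "to record lochia blood loss by pictorial blood assessment chart (PBAC), blood products, transfusion, and concomitant medications daily for up to 21 days". The Appendix has a PBAC row and a row headed "Diary: Blood products, transfusion, medications". The diary's contents are also described elsewhere in Section 3.2 and in inclusion criterion 5 (Section 4.3). None of these listings includes symptoms or adverse events.

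**Other routes.** Section 4.6 asks women to report safety problems or side effects linked to study drug. Section 5.0 (Local Adverse Event Reporting) has them report any adverse event to treatment-centre staff, and requires every event up to 30 days after administration to go on the CRF. An interim history is taken on Day 21.

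**The concern.** A table by onset or duration needs events to be found and dated with similar care throughout follow-up. Here the inpatient days have daily questioning plus a post-infusion check. The following 19 days have one visit at the end and a daily record that does not ask about adverse events.

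A mild headache on Day 1 will probably be recorded with its date. The same headache on Day 9, if untreated, is recorded only if the woman contacts staff or remembers it on Day 21. If it is remembered, its start, stop and summed duration are reconstructed.

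Safety and tolerability are secondary objectives. All arm comparisons are descriptive (Section 3.3), so these tables are themselves the safety result. The pilot is also meant to show that data collection works before a larger trial (Sections 3.2 and 3.3), so an uncorrected gap could carry forward.

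**Working it through.** The plan gives no event rate or capture figure for this point, so there is no stated number to reproduce.

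**1. Contact frequency** (visit days from Section 3.2 and the Appendix)
- Assessment days are 0, 1, 2 and 21, so the gaps are 1, 1 and 19 days.
- Days 0-2: 3 assessments / 3 days = 1.0 per day.
- Days 3-21: 1 assessment / 19 days = 0.053 per day. The ratio is 1.0 / 0.053 = 19.
- Days 3-21 are 19 of the 22 days to the last visit: 19/22 = 86%.
- Longest recall at Visit 5, for an event starting on Day 3: 21 - 3 = 18 days.

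**2. Recording window against last visit** (Section 5.0, Local Adverse Event Reporting)
- Thirty days after the Day 2 dose is Day 2 + 30 = Day 32. Days 22-32 are 11 days with no scheduled assessment.
- Counted from the Day 0 dose, the window ends on Day 30, leaving 9 such days.

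**3. Direction of the effect.** This is an illustration on assumptions that are not in the documents: a constant daily hazard h, full capture on Days 0-2, and a fraction c of events captured on Days 3-21.
- Early proportion of women with an event: 1 - exp(-3h).
- Late proportion: 1 - exp(-19hc).
- Both divide by women exposed, so late falls below early only if 19hc < 3h, that is, c < 3/19 = 16%, whatever h is.
- The per-dose rate behaves alike. The dose count is the same for both windows, so the late/early ratio of episodes is 19c/3, with the same break-even.
- Per day observed, the late/early hazard ratio is c, which is below 1 for any incomplete capture.

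| Assumed h per day | Early | Late, c = 1 | c = 0.5 | c = 0.25 | c = 0.1 |
|---|---|---|---|---|---|
| 0.01 | 3.0% | 17.3% | 9.1% | 4.6% | 1.9% |
| 0.02 | 5.8% | 31.6% | 17.3% | 9.1% | 3.7% |
| 0.05 | 13.9% | 61.3% | 37.8% | 21.1% | 9.1% |

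At h = 0.02 and 20 women, the early count is 20 × 0.058 = 1.2. With half of late events captured, the late count is 20 × 0.173 = 3.5 against a true 20 × 0.316 = 6.3. Late events are undercounted, yet the late figure still exceeds the early one. The table cannot show which part is timing and which is capture.

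**The case against.** The strongest reply is that late events are not left uncaptured. Women are asked to report problems, all events within the 30-day window belong on the CRF, and Visit 5 takes an interim history with a specific check for allergic reaction, thrombosis and other bleeding. Diary entries on lochia, transfusion and medications can help date bleeding and treated events. The tables are descriptive, and the success and feasibility criteria in Section 3.3 do not use onset timing. All of this stands, and it narrows the exposed group mainly to mild, untreated events and to the accuracy of onset and stop dates. None of these routes gives prompted, dated capture of such events between Day 2 and Day 21. The Section 4.6 request is also limited to effects linked to study drug, so a woman may filter by her own view of cause.

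A reader might infer more than the documents support:
- **That late rates must fall by design.** The denominators do not shrink or grow with the window, and the longer late window pushes the late proportion up.
- **That only 5% of late events are caught.** 1/19 is the share of days with a scheduled assessment, not a capture probability. Visit 5 asks about the whole interval.
- **That causality ratings are distorted.** The scales in Section 5.0 judge each event on its own timing and alternative explanations. The aggregate onset table is not an input.
- **That one arm is favoured.** Both arms have the same schedule, so uneven contact alone does not do this.

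**Conclusion.** The point holds as a limit on what the onset and duration tables can show. After Day 2, scheduled contact drops from once a day to once in 19 days, and the daily record has no adverse-event item. Mild untreated events starting on Days 3-20 therefore rest on self-report or on recall of up to 18 days. Whether late rates look lower or higher than early ones depends on the window, the denominator and the unknown capture fraction. The 16% break-even assumes a constant hazard and full early capture, and neither can be checked from the documents. No bias between arms is shown.

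The mismatch between the 30-day recording window and the last visit on Day 21 does not depend on those assumptions: 9 to 11 days of required recording have no scheduled contact. The diary finding rests on the listed contents, since the diary form itself is not reproduced in the document. This is an inexpensive improvement to data for a stated secondary objective. It is not a flaw in the primary comparison.

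**What to change.** 1. Add one daily line to the existing diary through Day 21: any adverse event, yes or no, with start and stop dates. Update the diary descriptions in Sections 3.2 and 4.3 and in the Appendix to match.
2. In the adverse events paragraph of Section 3.3, report onset by arm separately for Days 0-2 and Days 3-21. State that the two periods differ in ascertainment and are not to be read as a time trend. Changing the denominator to woman-days would not remove the need for this note, because incomplete late capture lowers a per-day rate directly.
3. Reconcile the 30-day recording window in Section 5.0 with the final visit on Day 21. State which dose starts the window and how events after Day 21 are to be found.

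Items 1 and 2 need one diary line and a few sentences of text, with no added visit or blood draw. The downside is slightly more diary burden and more minor events to classify. The cost of item 3 depends on how the passages are reconciled.

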
3.3 Data Collection and Statistical Consideration.

This is a pilot study comparing rVWF + TA vs. rVWF alone in subjects with Von Willebrand disease, and therefore, comparisons between arms will be descriptive, including mean, median, standard deviation, frequency and percentages. A sample size of at least 20 subjects should provide be sufficient to determine feasibility of enrollment, study drug administration, and data collection for a future phase III trial. Data will be collected by [name] and her research nursing staff. All data required by the study will be adequately documented in the source documents (hospital records, clinical and office charts, laboratory reports, subject diaries, pharmacy dispensing records).

The Primary Objective is to determine the efficacy of rVWF plus TA vs. rVWF alone in reducing postpartum hemorrhage in women with VWD. The Primary Endpoint is quantitative blood loss (QBL) at delivery. The Secondary Objectives are to evaluate the safety, tolerability, and mechanism of rVWF plus TA vs. rVWF alone in reducing postpartum hemorrhage in women with VWD.

The Secondary Endpoints include safety assessment by lochial blood loss by pictorial blood assessment chart (PBAC) blood products, transfusion, and hysterectomy within 21 days of delivery; and mechanism of PPH reduction by VWF assays, fibrinogen, and d-dimer with 21 days of delivery.

Analysis of endpoints. The Primary Endpoint is based solely on quantitative blood loss (QBL) at delivery obtained by the labor suite nurse and documented by hospital chart. The Secondary Endpoints are based on assessments of safety and the mechanism of hemostasis by rVWF and/or TA. Safety variables, including lochial blood loss by PBAC, blood products, transfusions, and other medications; and the mechanistic variables, including VWF assays (VWF:RCo, VWF:Ag, FVIII:C) and coagulation assays (fibrinogen and d-dimer) will be assessed at 1 day, 2 days, and 21 days postpartum, and where possible, compared with assessment at screening.

Descriptive statistics will be provided for the primary efficacy variable and secondary safety and mechanistic assessment variables, and also by treatment arms. The frequency distribution of the hemostatic and safety efficacy assessments will be presented for each of the study arms.

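### The only numeric success rule (at most 6 failures in 20) pools the two randomised arms, so it says nothing about tranexamic acid, and the power claim beside it has no stated numerical basis

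*Combined protocol and SAP*

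**What the plan says.** Section 3.3, under Sample Size and Power for Pilot Study, sets the success rule: "The study is considered successful if treatment of fewer than or equal to 6 of the 20 subjects is assessed ineffective or unsafe". Just before it stands the power claim, "The minimum planned sample size of 20 evaluable subjects also provides adequate power to" "evaluate the success and feasibility of the study", followed by a citation to reference 41. Feasibility is defined separately and without a number: "The study is considered feasible if procedures, i.e. recruitment, randomization, and study drug administration can be performed successfully".

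Earlier in section 3.3 the objective is comparative: "The Primary Objective is to determine the efficacy of rVWF plus TA vs. rVWF alone in reducing postpartum hemorrhage in women with VWD". The analysis is not inferential: "comparisons between arms will be descriptive, including mean, median, standard deviation, frequency and percentages". The sample size is justified by feasibility: "A sample size of at least 20 subjects should provide be sufficient to determine feasibility of enrollment". By-arm reporting is promised: "The frequency distribution of the hemostatic and safety efficacy assessments will be presented for each of the study arms". The Dosing Schema in section 3.2 allocates 10 women to each arm.

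**The concern.** The trial randomises women to rVWF with or without TA and asks whether adding TA reduces blood loss. Its one numeric verdict adds the failures from both arms together. The verdict is therefore the same whichever arm the failures fall in, and the word used for passing can sit beside by-arm tables that point the other way.

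Two further gaps affect the same paragraph. The plan does not define, for an individual woman, what counts as ineffective, unsafe or evaluable. The primary endpoint, quantitative blood loss (QBL), has no success cut-off, and the 1000 mL definition of postpartum hemorrhage (PPH) appears only in the background (section 2.1). The rule cannot be applied as written, and in an open-label trial definitions left open could be settled after results are known. Also, power is called adequate without a null rate, target rate, alpha or power value, so the claim cannot be reproduced.

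What is at stake is how the pilot's result is described to readers and to the planners of the next trial.

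**Working it through.** **The plan's own figure.** There is no power value to reproduce. The only numbers are the limit of 6, the total of 20 and the 10 per arm.

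**Assumed inputs.** No failure rate is stated. As stand-ins I use two PPH rates from section 2.1, 5.5% and up to one-third, with 20% as an assumed intermediate value. PPH is not the same as ineffective or unsafe, so every probability below is illustrative.

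**Step 1: the label (no assumed rates needed).** Let A and B be failures with and without TA, each out of 10. The rule passes when A + B ≤ 6, which is symmetric in A and B.

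| A (TA) | B (no TA) | Total | Label | Fisher exact p, two-sided |
|---|---|---|---|---|
| 6 | 0 | 6 | successful | 0.011 |
| 5 | 0 | 5 | successful | 0.033 |
| 3 | 3 | 6 | successful | 1.00 |
| 0 | 6 | 6 | successful | 0.011 |
| 0 | 7 | 7 | not successful | 0.003 |

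The Fisher test is not planned. I use it only to mark which splits are clear at this sample size.

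**Step 2: swapping the arms.** P(pass) = Σ over a = 0 to 6 of P(A = a) × P(B ≤ 6 − a), with A and B binomial on 10. Rates of one-third on TA and 5.5% without give 0.94. Rates of 5.5% on TA and one-third without also give 0.94.

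**Step 3: how often the label clearly contradicts the data.** Among passing splits with more failures on TA, only 5/0 and 6/0 reach p < 0.05.

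- One-third on TA, 5.5% without: [P(A=5) + P(A=6)] × P(B=0) = (0.1366 + 0.0569) × 0.945^10 = 0.1935 × 0.568 = 0.110.
- One-third on TA, 20% without: 0.1935 × 0.8^10 = 0.1935 × 0.1074 = 0.021.
- Equal rates of 5.5%, 20% or one-third: at most 0.003.
- Opposite direction (TA clearly better, labelled not successful), 5.5% on TA and one-third without: 0.018.

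**Step 4: what the power claim could mean.** With a common failure rate p, P(pass) = P(Bin(20, p) ≤ 6).

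| p | P(pass) |
|---|---|
| 5.5% | 0.9999 |
| 20% | 0.91 |
| 30% (the rule's own limit, 6/20) | 0.61 |
| one-third | 0.48 |

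A just-passing 6/20 has an exact (Clopper-Pearson) 95% CI of 12% to 54%.

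**Step 5: what 10 per arm can estimate.** The 95% CI half-width for a difference in mean QBL, in SD units, is t(0.975, 2n − 2) × √(2/n).

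- n = 10 per arm: 2.101 × 0.447 = 0.94 SD.
- n = 8 per arm: 2.145 × 0.500 = 1.07 SD.

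Exact 95% CIs for one arm: 0/10 gives 0% to 31%; 3/10 gives 7% to 65%; 6/10 gives 26% to 88%.

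**The case against.** The strongest reply is that pooling has a rationale in the protocol. Section 2.2 speaks of showing safety and tolerability with or without TA, and section 3.2 describes preliminary information on rVWF 80 IU/kg with or without TA in 20 women. Both arms receive the same rVWF regimen. A count over all 20 is then a sensible screen of overall acceptability, and indifference to arm is what such a screen should have. This stands as a possible reading. But section 3.3 does not say so: it attaches the count to the success of the study and places it beside a comparative objective.

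Safeguards elsewhere also limit the harm. Section 3.2 makes the phase III trial conditional on feasibility. Section 3.3 promises by-arm summaries. Section 5.0 halts enrollment for review by the data safety monitoring committee after a single anaphylaxis, thrombotic event, severe bleed or Grade 2 or greater allergic reaction, so a cluster of such events would be reviewed well before any final label. All of this stands.

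Four stronger readings are tempting, and the documents do not support them:

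- *The rule could send the wrong treatment into phase III.* It is not tied to that decision.
- *The plan claims power to compare the arms, or is deficient for lacking it.* The claim concerns success and feasibility, and arm comparisons are declared descriptive.
- *Contradictory labels are likely.* If any excess of 3 or more failures on TA counts as a contradiction, the figure is 51% at one-third against 5.5%. That assumes TA does much worse, which nothing in the protocol suggests, and it counts splits such as 3/0 (p = 0.21) and 4/1 (p = 0.30) that 10 per arm cannot distinguish from chance.
- *The power claim has no basis at all.* Reference 41 is cited, and its content cannot be judged from these documents. What is missing is a numerical basis in the plan.

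**Conclusion.** The point holds in a limited form and should be fixed. That the pooled rule cannot speak to the primary objective follows from its wording and needs no assumption. The consequence is a potentially misleading label, not a wrong decision about the next trial and not hidden arm data. A clear contradiction is uncommon: about 11% of trials under an assumed strong reversal (one-third on TA, 5.5% without), 2% with 20% without, and 0.3% or less with equal rates. These sizes rest on PPH rates standing in for an undefined failure and on Fisher p < 0.05 as the mark of a clear split.

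The power statement cannot be verified. Across the protocol's own PPH figures the chance of passing runs from near certainty to about one in two, so whether power is adequate depends on a failure rate that the plan never states. The undefined failure terms matter at least as much as the pooling, since without them neither a pooled nor a by-arm count can be made.

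**What to change.** Three changes to section 3.3:

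1. Delete the adequate-power wording. State, in line with the section's own justification, that 20 women were chosen for feasibility and that the trial is not powered to compare arms. Give the expected precision: a 95% CI half-width for the QBL difference of about 0.94 SD with 10 evaluable women per arm, or 1.07 SD with 8.
2. Stop using the pooled count as the verdict on success. Define before analysis, from data already collected, what makes a treatment ineffective or unsafe and who is evaluable. Keep in the count treated women who leave under the Study Termination paragraph of section 3.2. Report failures for each arm with exact 95% CIs and no per-arm pass limit. If the 6-of-20 count is kept, label it a trial-level acceptability screen for rVWF with or without TA that says nothing about the effect of TA.
3. Add the between-arm QBL difference with a 95% CI as the descriptive efficacy output. This is estimation, so the analysis stays descriptive.

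The cost is rewording, agreement on three definitions and a few intervals, with no extra women, visits or data. The sponsor loses or restricts one simple label, and the sample-size statement becomes less favourable.
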